8.0 Schedule of Assessments

The study-specific assessments are detailed below and are outlined in the Schedule of Assessments Table. Screening assessments must be performed within 21 days prior to the first dose of investigational product (unless otherwise specified). Screening assessments performed within 7 days of dosing may also be used as Day 1 assessments. Any results falling outside of the reference ranges may be repeated at the discretion of the investigator. All on-study visit procedures are allowed a window of \pm 7 days unless otherwise noted. Treatment or visit delays due to public holidays, weather conditions, or natural disasters, do not constitute protocol violations.

A signed, written, informed consent form must be obtained prior to screening assessments, and before any study-specific assessments are initiated.

Schedule of Assessments

Period/Procedure	Screening1	Treatment						Follow-Up
Week or Day Study Day	-21 to -1	Day 1	Every 2 weeks (until week 4)	Week 4 only	Every 4 weeks ²	Week 12 only	Every 16 weeks (after week 12)	End of Study Follow-up Assessments
Informed Consent	X							
Randomization	N/A							
Treatment								
Study drug		Study drug is taken orally once a day						
Clinical Procedures								
Medical History	X		X					
Physical Exam with weight	X	X	X		X			X
Vital Signs	X	X ³	X		X			X
Disease Assessment ⁴	X					X ⁵	X ⁵	X
ECOG Performance Status	X	X	X		X			X
EKG with QTc measurement	X			X		X	X	X
Laboratory Assessments ⁶	X				X			X
Liver Function Tests (LFT) ⁷	X		X ⁷		X ⁷			
Urinalysis	X				X			
Quantitative dipstick for urine protein ⁸	X				X			
Thyroid function (TSH, free T3 and free T4)	X							
Blood for CTC ⁹	X			X		X		X
Blood for cytokines ¹⁰	X			X				
Archival tumor tissue collection	X							
Tissue biopsy, Optional ¹¹	X							
Other								
Adverse Event Assessment		X	X		X			X
Con Meds	X	X	X		X			X

- ¹ All screening and baseline procedures must be completed within 21 days prior to the first dose of study medication
- ² If stable without grade 2 or greater toxicity
- ³ Subjects must have a pre-dose BP reading of \leq 150/90mmHg
- ⁴ CT of chest, abdomen and pelvis for subjects with measurable disease; CTMRI or Bone scan for subjects with bone only disease; Bone scan to be performed on all patients at screening. PET/CT can be used in place if CT scan is diagnostic
- ⁵ Unless indicated sooner by clinical findings
- ⁶ Blood urea nitrogen (BUN), Creatinine, Calcium, Potassium, Sodium, Glucose, Hematology: Hematocrit (HCT), Hemoglobin (HGB), Platelet count, White blood cell count (WBC), and differential are collected every 2 weeks until week 4, then every 4 weeks
- ⁷ Liver Function Tests (LFT) including Alanine aminotransferase (ALT), Aspartate aminotransferase (AST), Alkaline Phosphatase, Total Bilirubin and Albumin. Hematology: Hematocrit (HCT), Hemoglobin (HGB), Platelet count, White blood cell count (WBC), and differential. LFTs are collected every 2 weeks at weeks 3, 5, 7, and 9, then every 4 weeks and as clinically indicated.
- ⁸ UPC is required only if urine protein is $>$ 100.
- ⁹ CTCs will be collected at baseline, and then at 4 weeks, at 12 weeks and at the first visit documenting progression. One CellSave tube (7.5 ml) and one purple top tube (10 ml) should be sent at baseline, subsequent collections should include only one CellSave tube. Quantification of CTC will be conducted at [name] laboratory at UCSF
- ¹⁰ Serum will be collected at baseline and at 4 weeks. The cytokine levels will be measured by ELISA.
- ¹¹ Tissue biopsy is optional in this study, the safety of the biopsy will be determined by treating physicians.

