Note: Initiation or adjustment of antihypertensive medication(s) is permitted prior to study entry. Blood pressure must be re-assessed prior to start of study therapy. The mean SBP/DBP values must be $<140/90$ mmHg (OR 150/90mmHg, if this criterion is approved by Safety Review Team) in order for a subject to be eligible for the study.

14. History of cerebrovascular accident (CVA), pulmonary embolism or untreated deep venous thrombosis (DVT) within the past 6 months.
Note: Subjects with recent DVT who have been treated with therapeutic anti-coagulant agents for at least 6 weeks are eligible.
15. Major surgery or trauma within 28 days prior to first dose of study drug and/or presence of any non-healing wound, fracture, or ulcer not related to cancer (procedures such as catheter placement not considered to be major).
16. Evidence of active bleeding or bleeding diathesis.
17. Any serious and/or unstable pre-existing medical, psychiatric, or other condition that could interfere with subject's safety, provision of informed consent, or compliance to study procedures

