8.1 Screening Assessments

Eligible patients will have the following procedures performed within 3 weeks prior to study entry:

1. Medical history.
2. Physical examination including height (recorded only at baseline) and body weight.
3. Vital signs
4. Disease assessment (CT of chest, abdomen and pelvis for subjects with measurable disease; CT/MRI or Bone Scan for subjects with bone only disease, or PET/CT).
Bone scan to be performed on all patients at screening. PET/CT can be used in place if CT scan is diagnostic.
5. ECOG Performance Status
6. EKG with QTc measurement
7. Laboratory assessments including:
 - a. Clinical chemistry laboratory tests: Blood urea nitrogen (BUN), Creatinine, Calcium, Potassium, Sodium, Glucose, and
 - b. Hematology: Hematocrit (HCT), Hemoglobin (HGB), Platelet count, White blood cell count (WBC), and differential.
8. Liver Function Tests (LFT) including:
 - a. Alanine aminotransferase (ALT), Aspartate aminotransferase (AST), Alkaline Phosphatase, Total Bilirubin and Albumin.
9. Urinalysis with quantitative protein by dipstick. If > 100 by dipstick a UPC must be performed.
10. Thyroid function (TSH, free T3 and free T4).
11. Blood for circulating tumor cells.
 - a. One 7.5 ml CellSave tube, and one 10 ml purple top tube
12. Blood for cytokines
13. Archival tumor tissue collection: Paraffin-embedded tissue either at the time of diagnosis or disease relapse
14. Record all medication(s) received within 30 days prior to the first dose of study treatment and note if the medication is ongoing.

8.2 Pre-dose Assessments on Day 1

1. Physical examination (including body weight)
2. Vital signs (Subjects must have a pre-dose BP reading of $\leq 150/90\text{mmHg}$)
3. ECOG Performance Status
4. AE/SAE Assessments
5. Concomitant Medications

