8.3 Assessments During Treatment Period

8.3.1. Every 2 weeks until week 4

1. Medical History
2. Physical Exam including weight
3. Vital Signs
4. ECOG Performance Status
5. Adverse Event Assessment
6. Con Meds

If stable without grade 2 or greater toxicity, visits can be decreased to monthly after the first 4 weeks of therapy.

8.3.2. Every 2 weeks (weeks 3, 5, 7, and 9) until week 9

1. Liver Function Tests (LFT) including Alanine aminotransferase (ALT), Aspartate aminotransferase (AST), Alkaline Phosphatase, Total Bilirubin and Albumin.

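### Day 1 schedules no laboratory test and no CTC draw, so baseline liver, chemistry, haematology and CTC values may be 21 days old at first dose; the texts on the pre-dose blood pressure also need reconciling

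*Combined protocol and SAP*

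**What the plan says.** **Timing rules (8.0).** "Screening assessments must be performed within 21 days prior to the first dose of investigational product". "Screening assessments performed within 7 days of dosing may also be used as Day 1 assessments". "All on-study visit procedures are allowed a window of" plus or minus 7 days. Out-of-range results may be repeated if the investigator wishes. Section 11.1.2 lets drug be dispensed on Day 1 once eligibility is confirmed and the screening results have been reviewed.

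**Day 1.** The Day 1 column of the schedule and the list under "8.2 Pre-dose Assessments on Day 1" contain physical examination, vital signs, ECOG status, adverse events and concomitant medications. They contain no liver, chemistry or haematology test and no CTC sample.

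**Liver tests on treatment.** Footnote 7: "LFTs are collected every 2 weeks at weeks 3, 5, 7, and 9, then every 4 weeks", and as clinically indicated. Section 8.3.2 agrees: "Every 2 weeks (weeks 3, 5, 7, and 9) until week 9".

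**CTC and cytokines.** The baseline CTC sample belongs to screening (8.1, item 11); the next is at week 4. Section 8.5 requires the baseline cytokine serum within two weeks of study start. It sets no such limit for CTC. Section 12.1 names the impact of the combination on CTC as an exploratory endpoint.

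**Blood pressure.** Section 8.2 and footnote 3: "Subjects must have a pre-dose BP reading of" at most 150/90 mmHg. Note to exclusion 13 in 3.3: "Blood pressure must be re-assessed prior to start of study therapy".

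**The concern.** Every patient enters on documented progression, so liver values and CTC counts may be moving between screening and Day 1. The plan has a fresh clinical baseline at Day 1 but no fresh laboratory baseline. Three things depend on it.

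- **Liver events.** Table 3 uses the baseline level as one criterion of recovery (row C). Rows C and D also ask whether a rise is explained by the cancer. A pre-dose value up to three weeks old is weak evidence for either judgement. A patient who passed the 2.5 x ULN entry limit at screening could also exceed it by Day 1 without anyone seeing it.
- **CTC.** A change measured from a sample taken up to 21 days before pazopanib mixes time on the NSAI alone with time on the combination, while the endpoint concerns the combination.
- **Blood pressure.** Taken literally, the carry-over sentence in 8.0 covers vital signs, so a screening reading up to 7 days old could stand as the pre-dose reading. Sections 8.2 and 3.3 point the other way. Two sites could apply this differently.

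**Working it through.** The documents give no figure for these gaps, so there is nothing to reproduce. The check is calendar arithmetic.

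**Inputs**
- s, age of the screening sample at first dose: up to 21 days (8.0).
- d, days from first dose to the first on-treatment liver test: week 3 (footnote 7, 8.3.2). The documents do not say whether this means the start of the third week (14 days after first dose) or three elapsed weeks (21 days), so both are shown.
- w, visit window: up to +7 days (8.0).

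**Liver tests on either side of the first dose: gap = s + d, or s + d + w**

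| Screening test | d | Nominal | With +7 days |
|---|---|---|---|
| Day -21 | 14 | 21 + 14 = 35 | 42 |
| Day -21 | 21 | 21 + 21 = 42 | 49 |
| Day -7 | 14 | 7 + 14 = 21 | 28 |
| Day -7 | 21 | 7 + 21 = 28 | 35 |
| Day -1 | 14 | 1 + 14 = 15 | 22 |
| Day -1 | 21 | 1 + 21 = 22 | 29 |

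The permitted maximum is 35 to 42 days nominal and 42 to 49 days with the window. Of this, 14 to 21 days are on drug nominally, and at most 21 + 7 = 28.

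**Like-for-like comparison.** With the window applied at both ends, two-weekly liver tests may be 14 + 7 + 7 = 28 days apart and four-weekly tests 28 + 7 + 7 = 42. The fair comparison for 42 to 49 days is therefore 28 days for the early tests, not the nominal 14.

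**Source of the gap.** It comes from the 21-day screening window, the week-3 test and the visit window. The 7-day carry-over sentence plays no part, because Day 1 has no laboratory item for it to act on.

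**CTC, baseline to week 4**
- Sample at day -21: 21 + 28 = 49 days, of which 21 (21/49 = 43%) precede pazopanib. With +7 days: 56 days, 21/56 = 37.5%.
- Sample at day -14, the limit already used for cytokine serum: 14 + 28 = 42 days, 14/42 = 33%.
- Sample at Day 1 before dosing: 28 days, none before pazopanib.

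**Blood pressure, texts side by side**
- 8.0: a screening assessment within 7 days may serve for Day 1; no item is excepted.
- 8.2 and footnote 3: a pre-dose reading is required, attached to the Day 1 vital signs.
- 3.3 note: re-assessment before therapy, with no timing. It follows a sentence on adjusting antihypertensives, so it may concern only those patients.

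No text says which governs. The conflict between 8.0 and 8.2 remains even if the 3.3 note is set aside.

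**The case against.** The strongest reply is that any screening window lets values drift and that this plan has safeguards. Screening results are reviewed before dispensing, out-of-range results may be repeated, and patients are examined on Day 1. Clinic visits, chemistry and haematology are two-weekly until week 4, and liver tests may be added when clinically indicated. All of this stands, and it is why the point is minor. But repeats are optional, and none of these provisions requires a laboratory value fresher than 21 days.

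CTC is exploratory, and section 12.0 plans to correlate CTC with response and time to progression without defining a baseline-to-week-4 change. That stands too. However, 12.1 asks about the impact of the combination on CTC and section 1.3 speaks of following its reduction; both need a baseline.

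On blood pressure, the specific requirement in 8.2 can be read as overriding the general and permissive sentence in 8.0. That is a fair reading, but the plan does not state it.

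A reader might infer several stronger claims that the documents do not support:
- *There is no safety baseline.* Day 1 has examination, vital signs, ECOG status and adverse events. Only the laboratory part is missing.
- *Disease-related liver rises will be counted as pazopanib toxicity.* Table 3 row C excludes rises put down to malignancy, the bilirubin limb of row D excludes those due to progression, and rows B and C call for a work-up of other causes.
- *The interval across the first dose is the longest in the early schedule.* The EKG gap from week 4 to week 12 is 56 days, and the disease assessments may be 21 + 84 = 105 days apart.
- *The blood pressure check can be skipped.* This follows only if 8.0 overrides 8.2.

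**Conclusion.** The point holds as a minor design matter. Laboratory and CTC baselines may be 21 days old at first dose. The liver tests on either side of it may be 35 to 42 days apart nominally, or 42 to 49 days with the visit window. These are permitted maxima; how often they would occur cannot be told from the documents. If screening is done within 7 days of dosing, the gap is at most 28 to 35 days even with the window. The consequence is a weaker basis for Table 3's baseline and attribution judgements, not a rule that misclassifies events. For CTC, up to 21 of 49 days (43%) of a baseline-to-week-4 change can precede pazopanib. This assumes that the NSAI is continued through screening, as the description of treatment in 3.1 suggests, so those days are on the failing NSAI and not untreated. The blood pressure texts are unreconciled. Nothing here touches the primary endpoint, the sample size or the two-stage rule.

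**What to change.** 1. **CTC.** Move the baseline draw from 8.1 to the Day 1 visit before dosing, with the same tubes (one 7.5 ml CellSave, one 10 ml purple top), and amend the schedule and footnote 9. No extra visit or sample is needed.
2. **Laboratory baseline.** Define the baseline liver, chemistry and haematology value for the safety tables, and apply to it the 7-day limit that 8.0 already uses for Day 1 assessments. Add the tests to the Day 1 column and 8.2 on that footing. The cost is one routine draw at an existing visit, only for patients screened 8 to 21 days earlier. With a value no more than 7 days old, the maximum liver-test gap falls to 21 to 28 days nominal, or 28 to 35 with the window.
3. **Blood pressure.** Reconcile 8.0, 8.2 with footnote 3, and the 3.3 note in one sentence stating whether a screening reading may serve as the pre-dose reading, and to whom the 3.3 re-assessment applies. Which rule is right is a clinical decision for the sponsor and is not proposed here. The cost is wording only.

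It would also help to state in footnote 7 and 8.3.2 how many days after first dose week 3 falls.

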8.3.4 Every 4 weeks

1. Physical Exam including body weight
2. Vital Signs
3. ECOG Performance Status
4. Laboratory assessments including:
 - a. Clinical chemistry laboratory tests: Blood urea nitrogen (BUN), Creatinine, Calcium, Potassium, Sodium, Glucose, and
 - b. Hematology: Hematocrit (HCT), Hemoglobin (HGB), Platelet count, White blood cell count (WBC), and differential.
5. Liver Function Tests (LFT) including Alanine aminotransferase (ALT), Aspartate aminotransferase (AST), Alkaline Phosphatase, Total Bilirubin and Albumin.
6. Urinalysis with quantitative protein by dipstick. If > 100 by dipstick a UPC must be performed.
7. Adverse Event Assessment
8. Con Meds

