8.3.5 Week 12 only

1. Blood for CTC. One CellSave tube (7.5 ml) will be drawn.
2. Disease assessment (CT of chest, abdomen and pelvis for subjects with measurable disease [unless indicated sooner by clinical findings] or Bone Scan for subjects with bone only disease, or PET/CT). PET/CT can be used in place if CT scan is diagnostic.
3. 12-Lead EKG

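### The end-of-study visit schedules no liver function tests, and the general 7-day window is loose for the early two-weekly liver tests

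*Combined protocol and SAP*

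**What the plan says.** **End of study.** In the Section 8.0 table, the general laboratory row is marked under Follow-Up. The liver function row is marked only at screening, in the two-weekly column and in the four-weekly column. Section 8.4 agrees: its laboratory item covers urea nitrogen, creatinine, calcium, potassium, sodium, glucose and blood counts, with no transaminases, alkaline phosphatase or bilirubin. The same section follows patients for four weeks after removal (or to death, if earlier), records adverse events, and follows anyone removed for unacceptable toxicity until it resolves or stabilizes.

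**Early liver tests.** Footnote 7 to the table: "LFTs are collected every 2 weeks at weeks 3, 5, 7, and 9, then every 4 weeks and as clinically indicated". Section 8.3.2 repeats the first part: "Every 2 weeks (weeks 3, 5, 7, and 9) until week 9". Section "8.3.4 Every 4 weeks" lists the liver panel as well. The table's two-weekly mark sits in a column whose header begins "Every 2 weeks (until week 4", which read literally would put a draw at week 2.

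**Window and flexibility.** Section 8.0: "All on-study visit procedures are allowed a window of" plus or minus 7 days unless otherwise noted. No other tolerance is given for liver tests in the table, its footnotes, Section 8.3 or Table 3. Section 8.0 also says: "Any results falling outside of the reference ranges may be repeated at the discretion of the investigator". Section 8.3.1 adds: "If stable without grade 2 or greater toxicity, visits can be decreased to monthly after the first 4 weeks of therapy".

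**The concern.** Section 1.2 reports that hepatic dysfunction carries a boxed warning for pazopanib. Table 3 in Section 7.0 starts weekly liver tests only after a test has shown ALT above 3 x ULN. Below that level, row A relies on the protocol's own schedule. A symptomless rise is therefore found mainly through scheduled tests, and two features of the schedule weaken that.

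The main one is at the end of treatment. A patient who stops for progression or withdraws consent, with no recognized liver problem, attends a visit at which blood is drawn but liver enzymes are not on the list. A site following the plan exactly would not measure them.

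The lesser one is during weeks 3 to 9. A tolerance of 7 days either way is half of the 14-day interval it applies to. In the extreme, it lets the early two-weekly tests drift to the four-weekly spacing meant for later.

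What is at stake is how soon a silent liver signal is seen, and how complete the safety data are (a secondary objective). The primary endpoint, clinical benefit at 12 weeks, does not depend on either.

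**Working it through.** The documents state no maximum gap between liver tests, so there is no plan figure to reproduce. Week n is taken as day 7n.

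**1. Is the end-of-study omission real, or does chemistry include the liver panel?**

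| Section | Chemistry | Hematology | Liver panel |
|---|---|---|---|
| 8.1 Screening | listed | listed | listed separately |
| 8.3.4 Every 4 weeks | listed | listed | listed separately |
| 8.4 Follow-up | listed | listed | not listed |

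Where the protocol wants liver tests, it names them as their own item. The general chemistry list therefore cannot be read as containing them, and the table and 8.4 agree in leaving them out.

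**2. How old can the last liver test be when treatment stops?**

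- Nominal four-weekly spacing: up to 4 x 7 = 28 days.
- Compliant maximum, with the last test 7 days early and the next due 7 days late: 28 + 7 + 7 = 42 days.
- Stopping at a scheduled scan (weeks 12, 28, 44), with tests every 4 weeks from day 1 as in 8.3.4: a test is due the same week, so nominally 0 days.
- Stopping at the same scans, with tests counted on from week 9 as in footnote 7 (weeks 13, 17, 21, 25, 29, and so on): the last tests are at weeks 9, 25 and 41, so 3 x 7 = 21 days.

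**3. Early tests under plus or minus 7 days.** Worst gap = interval + 2 x window = 14 + 2 x 7 = 28 days.

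| Test | Nominal day | Allowed days, ±7 | Allowed days, ±3 |
|---|---|---|---|
| Week 3 | 21 | 14–28 | 18–24 |
| Week 5 | 35 | 28–42 | 32–38 |
| Week 7 | 49 | 42–56 | 46–52 |
| Week 9 | 63 | 56–70 | 60–66 |

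With these four tests alone, each adjacent pair can reach 28 days (14 to 42, 28 to 56, 42 to 70). Adding the 8.3.4 tests at week 4 (days 21–35) and week 8 (days 49–63) breaks up the first and third gaps. Only day 28 to day 56 remains. It needs the week-5 test on its earliest day, the week-7 test on its latest day, the week-4 test no later than day 28 and the week-8 test no earlier than day 56. A week-2 draw would not change this.

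The latest compliant first on-treatment test is day 21 + 7 = 28, or day 14 + 7 = 21 if the table's column means a week-2 draw.

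**4. Effect of a narrower window.** Using 14 + 2w: w = 1 gives 16 days, w = 2 gives 18, w = 3 gives 20. At w = 3 the bound is 52 − 32 = 20 days with the week-4 and week-8 tests counted. The latest first test is day 21 + 3 = 24, or day 14 + 3 = 17 with a week-2 draw.

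**The case against.** The strongest reply is that the plan already has event-driven cover. Section 8.4 follows patients for four weeks with adverse event recording and pursues unacceptable toxicity to its end. Footnote 7 allows extra liver tests on clinical grounds, abnormal results may be repeated, and monthly visits are open only to patients without grade 2 or greater toxicity. All of this stands and limits the harm. But each safeguard needs a prompt, and none schedules a liver test for a patient with no symptoms and no known abnormality.

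Earlier detection also changes less than it may seem. Under Table 3 row B, ALT between 3 and 8 x ULN without bilirubin elevation or hypersensitivity means continuing at the same dose with work-up and weekly tests. Stopping requires ALT above 8 x ULN, or above 3 x ULN with one of those features. Section 1.2 puts Grade 4 ALT elevation, and combined transaminase and bilirubin elevation, each below 1% in the cited pazopanib experience. Against this, the same section reports Grade 3 ALT elevation in 6% with renal-cell monotherapy and grade 3–4 transaminitis in three patients of the 20-patient breast cancer study. The gain is modest but not empty.

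On the window, the 28-day gap is a corner case. It is also arguable that a rule about visit procedures does not cover laboratory-only draws at weeks 5, 7 and 9 in patients on monthly visits. If so, those draws have no stated tolerance at all, which also calls for a sentence. No passage supports 3 days in particular; it is an example.

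A reader might infer that early tests will commonly be about four weeks apart. The documents do not support that: they say nothing about how draw days fall within the window, or whether a late draw shifts the next one, so no frequency can be given. A reader might also infer that the omission defeats the requirement in Section 16.2.2 to report serious events within 5 days of the last dose. That does not follow. Section 8.4 fixes no day for the visit, so an added panel would not guarantee a result in those 5 days, and 16.2.2 already requires possibly related serious events to be reported whenever they come to light.

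**Conclusion.** Both points hold, as a cheap improvement.

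The main point is that no liver test is scheduled at end of study. For a patient stopping between four-weekly tests without a known liver event, the last scheduled test may be up to 28 days old at nominal spacing; 42 days is the outer compliant limit. For stops at a scheduled scan the lag is nominally 0 or 21 days, depending on how the four-weekly count runs.

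The secondary point is that the general window permits 28 days between early tests due 14 days apart. With week-4 and week-8 tests counted, this is a rare permitted extreme reached in one configuration. It assumes that the general window applies to these draws and that week n means day 7n.

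The documents do not show how many liver events would fall in either gap, so no count of missed events is claimed. The design, sample size and primary analysis are unaffected.

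**What to change.** First, add the liver panel (ALT, AST, alkaline phosphatase, total bilirubin, albumin) to Section 8.4 and mark it in the Follow-Up column. It can be run on blood already drawn at that visit. With 30 patients planned and one panel each, the cost is at most about 30 panels, with no extra visit or draw.

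Second, add an exception in Section 8.0 giving liver tests through week 9 a tighter window, for example plus or minus 3 days, and say that it covers laboratory-only draws. This caps early gaps at 20 days; the cost is less scheduling slack in the first nine weeks. It leaves the later four-weekly spacing unchanged. The same amendment could state whether a week-2 liver draw is intended and from which week the four-weekly tests are counted.
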